## **6 Study Procedures**

### **6.1 Screening/Baseline**

The following procedures will be performed on all patients at screening:

- Informed consent
- Demographics (see section 6.4.1)
- Medical History (see section 6.4.1)
- Rutherford Classification (see Appendix B)
- ABI, TBI, TSP

- Measurement of wound size if Rutherford Classification Stage V or VI
- Vital signs (B/P, HR, temperature, respirations)
- The results of the following will be recorded from local laboratory tests that were performed in the month prior to screening: BUN, crt, Hgb, Hct, plt, INR, PTT, HbA1c, Tchol, tg, LDL and HDL.
- Urine pregnancy test for females of childbearing potential
- Recent angiographic data
- TcPO2 measurement (see section 6.4.2)
- SPP measurement
- Concomitant medications
- Randomization
- Dispense study drug

## **6.2 Month 3 follow up**

The patient will return to the clinic 3 months (90 days) after the date of randomization (+/- 2 weeks) and the following procedures will be performed:

- Rutherford Classification (see Appendix B)
- ABI, TBI, TSP
- Measurement of wound size and assessment of healing if Rutherford Classification Stage V or VI at Baseline
- Vital signs (B/P, HR, temperature, respirations)
- TcPO2 measurement (see section 6.4.2)
- SPP measurement
- Concomitant medications
- Dispense study drug
- Assess study medication compliance
- Collect SAEs and AEs

## **6.3 Month 6 follow up**

The patient will return to the clinic 6 months (180 days) after the date of randomization (+/- 2 weeks) and the following procedures will be performed:

- Rutherford Classification (see Appendix B)
- ABI, TBI, TSP
- Measurement of wound size and assessment of healing if Rutherford Classification Stage V or VI at Baseline
- Vital signs (B/P, HR, temperature, respirations)
- TcPO2 measurement

- SPP measurement
- Concomitant medications
- Assess study medication compliance
- Collect SAEs and AEs

Once a patient has been assessed at the 6-month follow-up visit they will exit the study. If ongoing use of ADP-receptor antagonist is required, patients will continue with either medication as indicated and approved although it will not be provided as part of the study. If no other indication exists for an ADP-receptor antagonist, either ticagrelor or clopidogrel will be discontinued, as per routine clinical practice.

#### **6.4 Study Procedures**

The following procedures will be considered as study procedures:

- TcPO2 measurement
- SPP measurement

Other procedures (Rutherford Classification, ABI, TBI, TSP, assessment of wound size and healing, vital signs, labs and angiographic procedures) are considered as SOC clinical procedures.

##### **6.4.1 Demographics and Medical History**

Demographic and medical history information to be collected include: age, race, gender, body-mass index, wound size, wound location, medical comorbidities including tobacco use history, duration of claudication, duration of lower extremity wound (if applicable), hypertension, hyperlipidemia, diabetes mellitus, prior cerebrovascular accident (CVA) or transient ischemic attack (TIA), carotid artery stenosis > 50%, chronic kidney disease (CKD), and complications related to prior PAD, such as prior wounds, forefoot amputation, below knee amputation, above knee amputation. Angiographic data relevant to revascularization procedures, including a record of arterial segment treated and vascular anatomy, will also be recorded.

##### **6.4.2 Measurement of TcPO2**

Assessment of TcPO2 will be performed using the Perimed Periflux System 5000 (Perimed Inc., Ardmore, PA) equipped with laser Doppler and transcutaneous oximetry function units. Before each measurement, the device will be calibrated as per manufacturer's specifications. Patients will be asked to refrain from tobacco use or caffeine 12 hours prior to TcPO2 assessment. All measurements will be performed in the supine position. A site distant from the diseased area (right subclavicular region) will be used as a reference value (12, 18).

Skin perfusion is strongly dependent upon skin temperature. Accurate and reproducible assessment of tissue oxygenation requires measurement at maximal hyperemia. Measurement at peak blood flow provides consistency of measurements at peak cutaneous blood flow reserve. Therefore, assessment of TcPO2 requires local tissue warming around the cutaneous ulcer site to

a prespecified temperature. As part of the Perimed system, the PF 5020 Temp Unit will be used to gradually warm the perimeter of the wound at sites of measurement to a steady state of 44°C (43-45°C) as per manufacturer specifications.

In patients with Stage IV (no wound) the level of the great toe will be used as the site for measurement of TcPO2. In the event of previous amputations, the most distal aspect of the foot will be used for the measurement. In order to ensure that subsequent assessments are consistent with the index measurement, the area used will be documented in the records

From room temperature (30-34°C), thermal steady state is achieved in 3-5 minutes and is maintained during tissue assessment. All subsequent TcPO2 assessments will be made at 44°C (43-45°C) to ensure maximal hyperemia and measurement accuracy. After the site of TcPO2 adhesion is prepared, the instrument is calibrated at thermal steady state (3-5 minutes). Continuous TcPO2 monitoring then commences over 10-15 minutes until transcutaneous oxygen pressure also reaches steady state.

Follow-up TcPO2 measurements (Perimed © Periflux System 5000) will be performed at 3 and 6 months after revascularization for the purposes of this study. Repeated measures for this study at 3 and 6 months are necessary to assess the interval change of TcPO2 and to provide additional accuracy of statistical modeling of secondary efficacy endpoints.

#### **6.4.3 Measurement of Skin Perfusion Pressure**

The skin perfusion pressure (SPP) is used to measure blood in the microcirculation around and within a wound using photoplethysmography with Doppler techniques and can be a useful predictor of wound healing potential. The SPP is performed by applying a pressure cuff to the extremity with the wound. Using a Doppler the measurement of the pressure at which perfusion first returns to the cutaneous microcirculation is obtained.

#### **6.4.4 Ankle-Brachial Index**

The ankle-brachial index (ABI) is a measurement that is the standard of care in the diagnosis of lower extremity PAD. The ABI also provides an objective baseline assessment that can be used to follow the progression of the disease process and evaluate the effectiveness of the disease plan. The ABI is performed by measuring the systolic blood pressure using a Doppler instrument from both brachial arteries and from both the dorsalis pedis and posterior tibial arteries after the patient has been at rest in the supine position for 10 minutes (23).

ABI measurement will be obtained at baseline, month 3 and month 6.

#### **6.4.5 Toe-Brachial Index and Toe-Systolic Pressure**

The toe-brachial index (TBI) and toe-systolic pressure are a more reliable indicator of limb perfusion in patients with diabetes or the elderly because the small vessels of the toes are often spared from the medial calcification that may occur in the leg arteries. A small occlusive cuff is placed on the proximal portion of the great toe (or another toe in the event of an amputation). A photo-electrode is placed on the end of the toe to obtain an arterial waveform using infrared light. The return of toe pulsatility is assessed by use of a plethysmographic detection device. The systolic pressure (TSP) is recorded at the point in which the baseline waveform is re-established. The ratio of the recorded toe systolic pressure (TSP) to the higher of

the two brachial pressures gives the TBI (23). TBI and TSP measurements will be obtained at baseline, month 3 and month 6.

## **7 Pharmacologic Loading Pre-revascularization**

For patients requiring revascularization, pharmacologic loading of an ADP-receptor antagonist will have been ordered as per standard of care so as to minimize risks for post-procedural arterial thrombosis. For this study, patients will have been treated with clopidogrel up to, during, and immediately after the time of revascularization as is standard of care. After revascularization, an ADP-receptor antagonist (e.g., clopidogrel) is routinely continued for 6 months, and then discontinued. Patients will be screened and randomized for the study either in the hospital after the procedure prior to discharge or at the time of the first out-patient clinic visit following revascularization (approximately one to two weeks after the procedure). Patients will be randomized to either clopidogrel or ticagrelor. After randomization patients will receive study medication (ticagrelor) with a 90-day provision through 6 months follow-up, refilled at the 3 month clinic visit.

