Similar to the endovascular treatment of coronary artery disease, percutaneous transluminal angioplasty (PTA) for PAD requires the use of dual-antiplatelet therapy (DAPT) to prevent thrombotic complications related to stent placement or balloon angioplasty. In a head-to-head comparison with clopidogrel among patients with acute coronary syndromes, ticagrelor has already shown impressive reductions in mortality without increasing the overall risk of major

bleeding (13). For patients undergoing PTA, DAPT is recommended for at least 30 days following the PTA procedure. The benefits of DAPT beyond 30-days after peripheral arterial intervention have been recently demonstrated; clopidogrel plus aspirin was superior to aspirin monotherapy for up to 6 months after PTA by preventing peri-procedural platelet activation and improved functional outcomes without increasing the risk of bleeding complications (14). Furthermore, even though costs associated with long-term DAPT are higher, clopidogrel has proven cost-effective over aspirin monotherapy for secondary prevention for vascular events among patients with PAD (15,16). With an anticipated antiplatelet benefit as robust as that of clopidogrel, ticagrelor may also demonstrate cost-effectiveness.

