### **5 Treatment of Patients**

#### **5.1 Treatment Regimen**

Patients are placed on clopidogrel after their arterial intervention per SOC. They will remain on clopidogrel up to the time that randomization occurs. For patients that are randomized to ticagrelor, the clopidogrel will be stopped.

Study Drug	Dose Level and Frequency
clopidogrel	75 mg by mouth daily
ticagrelor	90 mg by mouth twice daily

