## **5.3 Obtaining Study Drugs**

Study medication (ticagrelor) will be provided for the patients from randomization until the time of the 6 month visit.

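### A 90-day ticagrelor supply does not reach the latest permitted refill visit (day 104), and the visit windows and TcPO2 time origin disagree between sections

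*Combined protocol and SAP*

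**What the plan says.** On supply, section 7 states: "After randomization patients will receive study medication (ticagrelor) with a 90-day provision through 6 months follow-up, refilled at the 3 month clinic visit". Section 5.3 adds the commitment "Study medication (ticagrelor) will be provided for the patients from randomization until the time of the 6 month visit". The size of the refill is not given. Nor does the plan mention spare tablets, an early or mailed refill, or what happens to tablets left over at month 3.

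On visit dates, section 6.2 says "The patient will return to the clinic 3 months (90 days) after the date of randomization (+/- 2 weeks", and section 6.3 says "The patient will return to the clinic 6 months (180 days) after the date of randomization (+/- 2 weeks". The Study Visits table gives one week either side for the same two visits.

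On the clock, section 6.4.2 says follow-up TcPO2 measurements "will be performed at 3 and 6 months after revascularization for the purposes of this study". The synopsis and sections 6.2 and 6.3 count from randomization, which sections 4.1.1 and 7 allow up to about two weeks after the procedure.

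On background therapy, section 5.1 says "For patients that are randomized to ticagrelor, the clopidogrel will be stopped". Section 7 describes usual practice: "After revascularization, an ADP-receptor antagonist (e.g., clopidogrel) is routinely continued for 6 months, and then discontinued". Section 1.2 gives the minimum: "DAPT is recommended for at least 30 days following the PTA procedure".

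**The concern.** Two 90-day supplies add up to exactly 180 days, so the arithmetic works only if both visits fall on their nominal dates. The plan allows later dates. A fully adherent ticagrelor patient seen late but in window would have no study-supplied P2Y12 inhibitor for a time, because clopidogrel was stopped at randomization. At month 3 this comes after the 30-day minimum in section 1.2 but inside the six months that section 7 treats as routine, in patients recently treated with a stent or balloon.

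The gap would also fall just before a TcPO2 reading. Only ticagrelor is named as study-supplied, so a supply gap of this kind is confined to that arm. Under intent-to-treat the reading still counts and could dilute a ticagrelor effect. The compliance checks at both visits can detect a lapse but cannot prevent it.

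The conflicts in window and time origin are a lesser matter. They leave site staff unable to tell whether a visit on, say, day 100 is in window.

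**Working it through.** **Inputs.** Day 0 is randomization.
- First supply: 90 days (section 7), twice-daily dosing (section 5.1).
- Month-3 visit, day *a*: 76 to 104 (section 6.2), or 83 to 97 (Study Visits table).
- Month-6 visit, day *e*: 166 to 194 (section 6.3), or 173 to 187 (table).
- Refill: not stated; **assumed** 90 days for the month-6 check only.
- Lag from procedure to randomization: 0 to 14 days (sections 4.1.1 and 7).

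Every dose is assumed taken. The counts below are of permitted calendar dates, equally weighted. They do not forecast attendance.

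**Step 1: the plan's own figure.** 2 × 90 = 180 days, which equals the nominal month-6 date. It reproduces with no visit deviation.

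**Step 2: month 3, from stated figures only.** Gap = max(0, *a* − 90).
- Two-week window: days 91 to 104 have a gap, 14 of 29 days; the largest is 104 − 90 = 14 days.
- One-week window: days 91 to 97, 7 of 15 days; the largest is 97 − 90 = 7 days.

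**Step 3: month 6, assuming a 90-day refill.** Gap = max(0, *e* − end of supply).
- Leftovers kept: end = max(90, *a*) + 90.
- Leftovers collected: end = *a* + 90.

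Two-week window, 29 × 29 = 841 visit pairs:
- Kept: for *a* = 76 to 90 (15 days) supply ends on day 180, so *e* = 181 to 194 falls short: 15 × 14 = 210 pairs. For *a* = 91 to 104 the shortfall days number 13, 12, …, 0, which sum to 91. Total 210 + 91 = 301.
- Collected: the shortfall days number 28, 27, …, 0 as *a* runs from 76 to 104, which sum to 406.

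One-week window, 15 × 15 = 225 pairs:
- Kept: 8 × 7 + (6 + 5 + … + 0) = 56 + 21 = 77.
- Collected: 14 + 13 + … + 0 = 105.

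| Window | Leftovers | Pairs with a month-6 gap | Largest gap |
|---|---|---|---|
| ± 2 weeks | kept | 301/841 (36%) | 14 days |
| ± 2 weeks | collected | 406/841 (48%) | 28 days (*a* = 76, *e* = 194) |
| ± 1 week | kept | 77/225 (34%) | 7 days |
| ± 1 week | collected | 105/225 (47%) | 14 days |

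The worst cases at the two visits do not coincide. If *a* = 104, supply lasts to 104 + 90 = 194 and the month-6 gap is zero.

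**Step 4: time origin.** With a lag of 0 to 14 days, six months after revascularization is day 166 to 180 after randomization. That always lies inside ± 2 weeks (166 to 194). It lies 1 to 7 days outside ± 1 week (173 to 187) when the lag is 8 to 14 days. The same offset applies at month 3.

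**Step 5: do the remedies close the gaps?**
- 104 + 90, kept, ± 2 weeks: supply reaches day 104, then max(104, *a*) + 90 = 194. No gap at either visit.
- 97 + 90, kept, ± 1 week: supply reaches day 97, then day 187. No gap.
- 104 + 90, collected: end = *a* + 90 again, so 406 of 841 pairs still fall short. The leftover rule therefore has to be written down.
- Collected, refill sized for the earliest visit: 194 − 76 = 118 days (± 2 weeks) or 187 − 83 = 104 days (± 1 week). No gap.

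**The case against.** The strongest reply is that the only gap resting on stated figures is the one before month 3, and that TcPO2 reading is a secondary endpoint. After a refill on day 104, at least 166 − 104 = 62 days pass before the earliest month-6 visit. A gap before the primary reading needs a 90-day refill, which the plan does not state, and section 5.3 and the same sentence of section 7 both point to a refill meant to last to that visit. This stands, and the month-6 figures are conditional for that reason.

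The 90 days may also be nominal, since section 6.2 equates three months with 90 days and nothing forbids spare tablets. That reading would close the gap, but the plan does not say it, while it does explicitly permit later visits.

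The trial is open-label with marketed drugs, so a clinician could bridge a late patient by prescription, and concomitant medications are recorded at both visits. Section 9.2 already allows for non-adherence and 5% crossover. How clopidogrel is refilled is not described, so lapses in the control arm are equally unexamined. These points are fair. They are why no size or net direction of bias is claimed. They do not remove the mismatch between the quantity and the window.

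The 48% and 28-day figures also require leftovers to be collected, on which the plan is silent. They mark an outer bound.

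**Conclusion.** The concern holds, as a minor point. From stated figures alone, with full adherence, the first ticagrelor supply can end up to 14 days before a permitted refill visit (7 days under the table's window), contrary to section 5.3. The month-6 shortfall of up to 14 days, or 28 if leftovers are collected, rests on an assumed 90-day refill.

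The documents do not show that any patient will be off drug. They give no time course for loss of effect, so the effect on TcPO2 cannot be sized. Sample size and power are unaffected.

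The window and time-origin conflicts are real but should matter little on their own. No rule excludes out-of-window readings, the synopsis and visit sections agree on randomization, and the lag should balance between arms.

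**What to change.** - **Supply.** Keeping the two-week window, dispense 104 days of ticagrelor at randomization and 90 days at month 3, and state that patients keep leftover tablets. If the one-week window is chosen, dispense 97 and 90 days.
- **If leftovers must be collected,** keep the 104- or 97-day first supply and size the refill to the last permitted month-6 day: 194 minus the refill day (90 to 118 days), or 187 minus the refill day (90 to 104 days) with one week.
- **Window.** Use the same window in the Study Visits table and in sections 6.2 and 6.3.
- **Time origin.** In section 6.4.2, time TcPO2 at 90 and 180 days after randomization.
- **Continuation.** State that both assigned drugs continue through the month-6 TcPO2 reading. Section 6.3 largely implies this already.

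The cost is a few wording edits and some tablets. With leftovers kept it is 14 extra days per ticagrelor patient, 14 × 2 × 30 = 840 doses for 30 patients, or 7 × 2 × 30 = 420 with one week. With leftovers collected, the ceiling is (14 + 28) × 2 × 30 = 2,520 doses, or (7 + 14) × 2 × 30 = 1,260, reached only if every patient attends month 3 on the earliest day. The downside is some unused drug to account for.

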## **8 Safety Monitoring and Reporting**

An adverse event is the development of an undesirable medical condition or the deterioration of a pre-existing medical condition following or during exposure to a pharmaceutical product, whether or not considered causally related to the product. The term AE is used to include both serious and non-serious AEs.

An important medical event is any AE that may not result in death, be life-threatening, or require hospitalization but may be considered an SAE when, based upon appropriate medical judgment, it may jeopardize the patient and may require medical or surgical intervention to prevent one of the outcomes listed in the definitions of SAEs.

### **8.1 Adverse Events**

The following adverse events will be collected from the time that informed consent is obtained for this study:

- Self-reported shortness of breath
- Symptomatic bradycardia defined as self-reported symptoms of shortness of breath, chest discomfort, or dizziness with a confirmed heart rate of < 45 bpm at the time of the symptoms.
- Adverse events that are not listed in the current labeling for the drugs (see Appendix A and Investigator Brochure for ticagrelor).
- Events that lead to discontinuation of drug or result in a dose modification.

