Prohibited Medications	
 
• Concomitant use of oral anticoagulation with a vitamin K antagonist, factor Xa inhibitor, or direct thrombin inhibitor
 
• Aspirin > 100mg per day
 

Endpoints	
Primary endpoint
 
 
• Absolute change in TcPO2 from baseline to 6 months
 
 
Secondary endpoints
 
 
• Rate of wound healing from baseline to month 6 in treatment groups for patients with Rutherford Stage V-VI PAD
 
• Change in ankle-brachial index (ABI), toe-brachial index (TBI), toe-systolic pressure (TSP) and skin perfusion pressure (SPP) from baseline to month 6 in treatment groups
 
• Major adverse limb events including a composite of surgical limb loss or any major vascular repeat revascularization, including thrombectomy, thrombolysis, or major lower-extremity surgical procedure from baseline to month 6 in treatment groups
 
• Percent change in TcPO2 from baseline to 6 months
 
• Percent change and absolute change in TcPO2 from baseline to month 3
 

AE/ SAE Collection	
AEs
 
 
• Self-reported shortness of breath with symptomatic bradycardia
 
• Events that are not listed in the current labeling for the drugs
 
• Events that lead to discontinuation of drug or result in a dose modification
 
 
SAEs
 
 
• Death.
 
• Life threatening AEs.
 
• Requires inpatient hospitalization or prolongation of existing hospitalization.
 
• A disability/incapacity.
 
• A congenital anomaly/birth defect in the offspring of a patient who received drug.
 
• Important medical event that may jeopardize the subject or may require medical intervention to prevent one of the outcomes listed above.
 
 
Other SAEs of Special Interest
 
 
• Major bleeding defined as a composite of fatal bleeding, intracranial bleeding, hypovolemic shock or severe hypotension due to bleeding requiring pressors, or need for transfusion of at least 2 units in any 24-hour period.
 
• Major adverse limb events (surgical limb loss, major repeat revascularizations including thrombectomy, thrombolysis, or major lower extremity surgical procedure.
 

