## Study Visits

Study Procedures	Screening/ Baseline	3 Months (+/- 1 week)	6 Months (+/- 1 week)
Informed Consent	X		
Demographics	X		
Medical History	X		
Rutherford Classification	X	X	X
ABI, TBI, TSP	X	X	X
Wound Size	X	X	X
Vital Signs	X	X	X
Record Baseline Labs 	X		
Urine Pregnancy Test 	X		
Angiographic Data	X		
TcPO2 measurement	X 	X	X
SPP measurement	X	X	X
Concomitant Medications	X	X	X
Randomization	X		
Dispense Study Drug	X	X	
Assessment of wound healing		X	X
Study medication compliance		X	X
Collect AEs & SAEs		X	X

Baseline labs will be obtained from local labs performed in the month prior to screening and include the following: Blood urea nitrogen, creatinine, HbA1c, hemoglobin, hematocrit, platelet count, international normalized ratio, partial thromboplastin time, total cholesterol, low-density lipoprotein, high-density lipoprotein, triglycerides

For females of childbearing potential

Post angiography

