## **8.5 Safety Monitoring**

Safety endpoints to be assessed include major bleeding and self-reported dyspnea and self-reported symptomatic bradycardia. Major bleeding is defined as a composite of fatal bleeding, intracranial bleeding, hypovolemic shock or severe hypotension due to bleeding requiring pressors, or need for transfusion of at least 2 units in any 24-hour period. Self-reported symptomatic bradycardia is defined as self-reported symptoms of shortness of breath, chest discomfort, or dizziness with a confirmed heart rate of < 45 bpm at the time of the symptoms.

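### Dyspnea and symptomatic bradycardia, two of the three named safety endpoints, are likely to be poorly ascertained as the plan specifies them

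*Combined protocol and SAP*

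**What the plan says.** Section 8.5 states: "Safety endpoints to be assessed include major bleeding and self-reported dyspnea and self-reported symptomatic bradycardia". Section 9.1 compares safety endpoints between arms with Fisher's exact test.

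**Dyspnea.** In section 8.1 the item is simply "Self-reported shortness of breath", with no rule on onset or change. The general definition in section 8 covers a new condition or "the deterioration of a pre-existing medical condition following or during exposure to a pharmaceutical product". Section 6.4.1 begins: "Demographic and medical history information to be collected include: age, race, gender, body-mass index, wound size, wound location". It goes on to list comorbidities, but names no dyspnea, lung disease or heart failure. The baseline procedures in section 6.1 have no dyspnea item either. Section 4.1.2 excludes lung disease only when it is severe COPD that needs oxygen at home.

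**Timing.** Section 8.1 opens with "The following adverse events will be collected from the time that informed consent is obtained for this study". The row "Collect AEs & SAEs" in the Study Visits table is marked at months 3 and 6 and not at baseline.

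**Bradycardia.** Sections 8.1 and 8.5 require a self-reported symptom (breathlessness, chest discomfort or dizziness) "with a confirmed heart rate of < 45 bpm at the time of the symptoms". Heart rate is part of the vital signs at baseline, month 3 and month 6 (sections 6.1 to 6.3). No other study heart rate is listed.

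**Synopsis.** The AE/SAE row has a single item, "Self-reported shortness of breath with symptomatic bradycardia". The synopsis row on safety evaluations lists the two separately, as sections 8.1 and 8.5 do.

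**The concern.** A rule that counts new or worsened dyspnea needs the patient's status before treatment. The plan names no such record, so at month 3 the site must ask the patient to recall whether breathlessness preceded the study drug. Patients know their treatment (section 4.2), so recall may differ by arm. If stable prior dyspnea is counted as an event, it adds similar numbers to both arms and dilutes the comparison.

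The bradycardia definition asks for a heart rate that the study does not plan to obtain between visits. A symptomatic patient with no recorded rate does not meet it. A report of few or no cases could then mean that the event was rare, or that rates were missing, and the plan provides no count to tell these apart.

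At stake is whether two of the three named safety comparisons can be interpreted. The primary endpoint is not affected.

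**Working it through.** No stated figure is in dispute. The check sets the passages side by side, then adds one illustration.

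**1. Dyspnea.** Needed under section 8: status before exposure. Named in sections 6.1 and 6.4.1: none (respirations are a vital sign, not a symptom). Excluded at entry: only severe COPD on home oxygen, so patients with milder breathlessness can enter. First marked collection: month 3. The split between new, worsened and stable dyspnea therefore rests on recall over about three months.

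**2. Bradycardia.** Needed: symptom and rate together. Scheduled study rates after randomization: two, at months 3 and 6. No interim visit, call, ECG or confirmation rule is given. Other source: section 11.1 accepts patient reports and medical records, so a rate from an emergency or clinic record can count. Symptoms without a rate: breathlessness is still recorded as dyspnea. Dizziness or chest discomfort is recorded only if it is serious (section 8.2), unlabeled, or leads to discontinuation or a dose change (section 8.1).

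**3. Worst-case dilution on assumed rates.** Let b be the share with stable prior dyspnea and p the true rate of new dyspnea, taken as independent of b. If every prior case is counted, the observed rate is 1 − (1 − b)(1 − p) = b + (1 − b)p. For p = 0.15 and b = 0.10 this is 0.10 + 0.90 × 0.15 = 0.235; for p = 0.05 it is 0.10 + 0.90 × 0.05 = 0.145; the ratio is 0.235/0.145 = 1.62. Power is for an exact two-sided Fisher test at 0.05 with 30 per arm (sections 9.1 and 9.2). The values of b and p are assumptions; the documents give none.

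| True rates | b | Observed rates | Difference (points) | Ratio | Power |
|---|---|---|---|---|---|
| 15% v 5% | 0 | 15.0% v 5.0% | 10 | 3.0 | 9.3% |
| | 10% | 23.5% v 14.5% | 9 | 1.62 | 7.8% |
| | 20% | 32.0% v 24.0% | 8 | 1.33 | 6.3% |
| | 30% | 40.5% v 33.5% | 7 | 1.21 | 5.0% |
| 30% v 5% | 0 | 30.0% v 5.0% | 25 | 6.0 | 63% |
| | 10% | 37.0% v 14.5% | 22.5 | 2.55 | 41% |
| | 20% | 44.0% v 24.0% | 20 | 1.83 | 28% |
| | 30% | 51.0% v 33.5% | 17.5 | 1.52 | 20% |

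The difference shrinks by the factor 1 − b; the ratio shrinks much faster. At 15% v 5% the test has little power even with no dilution. Dilution costs appreciable power only if the true difference is large.

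**The case against.** A reader might infer that the two endpoints cannot be measured on this schedule. The documents do not support that. Both are adverse events collected as they are reported, not visit measurements, and section 11.1 accepts medical records. For the same reason, two visit days out of about 180 is not a measure of how much bradycardia would be found: it ignores rates recorded elsewhere.

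The new-or-worsened rule is already in section 8, and a patient can be asked at month 3 when breathlessness began. The table above therefore shows full misclassification, not the expected result. This stands, and is why it is only a worst case.

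The history list in section 6.4.1 is open-ended, and the case report form and its completion guidelines are separate documents. A dyspnea item may exist there. Even so, the protocol does not require one. The missing baseline mark in the adverse event row can also be read harmlessly, since month 3 can collect events since consent. That removes most of the conflict but leaves the reliance on recall.

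Requiring a confirmed rate is a legitimate choice for specificity, since dizziness with no rate is not bradycardia. This stands: the definition should be kept, and only the unconfirmed episodes made visible.

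Finally, with 30 per arm the safety tests are weak whatever is done. True, but a pilot's safety results are read mainly as counts, and these counts should be interpretable.

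**Conclusion.** The point holds as one of ascertainment. Dyspnea lacks a specified baseline status, so new or worsened cases depend on unblinded recall. Bradycardia lacks a planned source for the heart rate its definition requires between visits, so under-counting is likely and a low count is ambiguous.

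The size cannot be derived from the documents. If all stable prior dyspnea were counted, assumed true rates of 15% v 5% would give a ratio between 1.62 and 1.21 instead of 3.0 for 10% to 30% prior dyspnea. At an assumed 30% v 5%, power would fall from 63% to as low as 20%. Actual dilution should be smaller to the extent that sites apply section 8.

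A reader might also infer that both weaknesses must make the arms look alike. Dilution acts in that direction, but open-label self-report could shift dyspnea reporting in one arm, so the net direction is uncertain. The harm is lost interpretability of two safety comparisons in a 60-patient pilot. The baseline question is worth adding because pre-treatment status cannot be recovered reliably later.

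**What to change.** 1. Ask one dyspnea question at the baseline visit, before randomization, in the same words as at months 3 and 6. Count dyspnea as new or worsened from that answer, in line with section 8.
2. Mark adverse event collection from consent in the Study Visits table, to match section 8.1.
3. Keep the bradycardia definition and state which records count as confirmation. At months 3 and 6, record episodes of dizziness, chest discomfort or breathlessness together with any available heart rate. Report by arm, as a descriptive line, the symptomatic episodes with no heart rate available.
4. Reconcile the merged synopsis item with the separate items in sections 8.1 and 8.5, so that dyspnea without bradycardia is not omitted.

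The cost is one baseline question, one short form field, one table mark and one descriptive line, all at existing visits. The downside is that the line for episodes without a heart rate is less specific and should not be read as bradycardia.
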